#### Secondary outcomes

The other short-term efficacy outcomes will be analyzed similarly to the primary outcome.

### 7.4.4 Long Term Efficacy Analysis

#### Primary Outcome

The analysis of the primary long-term efficacy outcome, apical fractional area change 12 months post-surgery, will be analyzed like the primary outcome of short-term efficacy, regarding both primary and secondary analyses.

#### Secondary Outcomes

Quantitative long-term outcomes will be analyzed like the primary long-term efficacy outcome of apical fractional area change. Yes/no outcome variables like “able to undergo Stage III palliative surgery” will first be analyzed by describing percent by group and the groups

compared using a chi-square test. We will analyze time-to-event outcomes, like time to listing for cardiac transplant or death, first describing naïve rates with the Kaplan-Meier method and then using Cox regression models including terms for treatment group and baseline cardiac function. If the primary analysis suggests dependency of treatment on cardiac function, we will also repeat these analyses considering cardiac function as an effect modifier by including interaction terms between group and baseline cardiac function.

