**CLINICAL STUDY SUMMARY**

Title	Phase IIb Study of Intramyocardial Injection of Autologous Umbilical Cord Blood Derived Mononuclear Cells during Stage II Surgical Repair of Hypoplastic Left Heart Syndrome (AutoCell-II)
Running Title	Phase IIb Efficacy Study of UCB-MNC Intramyocardial Injection for HLHS and HLHS Variants
Protocol Number	CSP-4401
Phase	Phase IIb
Study Design	Prospective, Open label, Non-randomized, Observational Study
Overall Study Duration	6 years
Subject Participation Duration	Up to 4 years or until pre-operative work-up for Stage III surgical palliation has been completed or until cardiac transplant, whichever is first
Single or Multi-Site	Multi-Site
Objectives	This study will evaluate the efficacy and safety of UCB-MNC intramyocardial injections performed during Stage II surgical palliation by focusing on short and long-term cardiac function leading up to the pre-operative work-up for Stage III surgical palliation.
Study Purpose	Determine if the delivery of the autologous UCB-MNC product into the myocardium of the right ventricle of the heart at the time of Stage II surgical repair will provide a short-term improvement in cardiac function, while also providing a reduction in the cumulative days of hospitalization following Stage II surgical repair. Additionally, long-term improvement in cardiac function, growth, reaching Stage III surgical repair pre-op work-up and prolonging time to cardiac transplantation or death will be determined. Reaching developmental milestones and quality of life will also be monitored.
Number of Subjects	30-50 treated subjects receiving cell product, along with 30-50 subjects with standard surgical treatment (not receiving cell product).
Study Population	Subjects less than 13 months of age with HLHS or HLHS variant who are undergoing Stage II surgical palliation.
Study Product, Dose, Route, Regimen	The investigational product is autologous MNC derived from UCB at a concentration of 10-30 million TNC per mL. The investigational product will be delivered into the right myocardium via sub-epicardial injections of 0.1 mL per kg body weight to achieve the target dose of 1-3 million TNC per kg body weight.
Time and Duration of Administration	A single treatment will be administered intraoperatively upon the successful completion of the planned Stage II surgical repair.

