Primary and Secondary Long-Term Endpoints	
The primary long-term efficacy endpoint regarding the cell product and its delivery procedure is:
 
Change in right ventricular cardiac function at 12 months post-Stage II surgery compared to baseline, measured by echocardiogram.
 
Secondary long-term safety and efficacy endpoints in their order of relevance and importance in this clinical study are:
 
 
1) Change in weight every 6 months post-Stage II surgery compared to baseline.
 
2) Change in heart failure medication taken every 6 months post-Stage II surgery compared to baseline.
 
3) Change in arrhythmia medication taken every 6 months post-Stage II surgery compared to baseline.
 
4) Success of subject being scheduled for Stage III surgical repair.
 
5) Time (days) until listed for cardiac transplantation, or death following the 6-month follow-up.
 
6) Change in right ventricular function at Stage III surgery pre-op work-up compared to baseline, obtained by echocardiogram and cardiac catheterization.
 

Statistical Methodology	
Quantitative outcomes, like FAC, at specified time post-surgery, will be analyzed using analysis of covariance to estimate the difference in means between the cell-based therapy and control groups after adjusting for the baseline value (the measured value of the same variable, e.g. FAC, at the time of Stage II surgery). Categorical outcomes, like able to undergo Stage III palliation surgery, will be compared between groups using a chi-square test. Time-to event outcomes, like time until listing for cardiac transplant, will be compared using the Kaplan-Meier method and log-rank test. We will similarly do analyses of other variables based upon this patient subset. In secondary analyses we will also fit models which allow the treatment effect (mean difference between the cell-therapy group control groups) to depend on baseline cardiac function measures or other baseline values. This will be done by using the linear, logistic and Cox regression models as appropriate.

Imaging Core Lab	
M. [name] (Core Lab Director) Mayo Clinic Pediatric and Adolescent Medicine [name] [name]

Contract Manufacturing Organization	
ReGen Theranostics, Inc. [name] [name]

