### 3.3 Long Term Endpoints

The primary long-term efficacy endpoint regarding the cell product and its delivery procedure is:

Change in right ventricular cardiac function at 12 months post-Stage II surgery compared to baseline, measured by echocardiogram.

Secondary long-term efficacy safety endpoints in their order of relevance and importance in this clinical study are:

- 1) Change in weight every 6 months post-Stage II surgery compared to baseline.
- 2) Change in heart failure medication taken every 6 months post-Stage II surgery compared to baseline.
- 3) Change in arrhythmia medication taken every 6 months post-Stage II surgery compared to baseline.

- 4) Success of subject being scheduled for Stage III surgical repair.
- 5) Time (days) until listed for cardiac transplantation, or death following the 6-month follow-up.
- 6) Change in right ventricular function at Stage III surgery pre-op work-up compared to baseline, obtained by echocardiogram, cardiac MRI, and cardiac catheterization.

Additional variables may be assessed in an exploratory manner.

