#### Lost to follow up

Follow up times for subjects who are in study at the time of analysis will be censored in time-to event analysis, as with time until listing for cardiac transplant. Since the outcome regarding time to listing includes death as part of a compound outcome, there will be no censoring for death. In case of lost to follow up before time of analysis subjects will be censored, unless the investigators feel the subject could have been indicated for transplant in which case they will be included as such in the analysis.

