## 7.4 Analysis

### 7.4.1 Interim Analysis

This study has 5 planned safety and efficacy interim analysis planned. An interim analysis will be performed according to statistical analysis plan on all enrolled subjects after 10, 20, 30, 40 and 50 subjects have been treated and completed the 3-month follow-up visit. Results will be reviewed by the DSMB.

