### 7.4.2 Final Analysis

The final analysis of the study will be completed no later than after 50 subjects have completed both Treatment (Arm A) and Control (Arm B) of the study. However, the Sponsor may determine according to interim analysis results that both safety and efficacy endpoints have been achieved for the Phase IIb study. The Sponsor can make this determination at any time following the first interim analysis timepoint.

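### Reaching Stage III is tested by an unadjusted chi-square with no assessment time and no rule for children still in follow-up, so children not yet due may count as failures

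*Combined protocol and SAP*

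**What the plan says.** **Endpoint.** Section 3.3 lists it as "Success of subject being scheduled for Stage III surgical repair". Section 7.4.4 gives as its example of a yes/no outcome "able to undergo Stage III palliative surgery". Section 2 speaks of reaching the Stage III pre-operative work-up. None of the three gives a time at which status is read.

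**Test.** Section 7.4.4 (Secondary Outcomes) and the Clinical Study Summary describe percentages by group, which are then "compared using a chi-square test". The Summary adds secondary models of effect modification by baseline values, using "linear, logistic and Cox regression models as appropriate". Section 2 says the ability to reach Stage III work-up will be evaluated with adjustment for baseline.

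**Follow-up.** Each child participates "Up to 4 years or until pre-operative work-up for Stage III surgical palliation has been completed or until cardiac transplant, whichever is first"; the overall study duration is 6 years. Under Lost to follow up in Section 7.3, "Follow up times for subjects who are in study at the time of analysis will be censored in time-to event analysis". No parallel rule is given for yes/no outcomes. Section 7.2 analyses everyone with follow-up data (in the treated arm, after full delivery) and sets no minimum follow-up.

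**Timing.** Interim analyses occur once 10, 20, 30, 40 and 50 subjects "have been treated and completed the 3-month follow-up visit". Section 7.4.2 lets the Sponsor conclude that the safety and efficacy endpoints have been met: "The Sponsor can make this determination at any time following the first interim analysis timepoint". The latest final analysis is tied to 50 subjects completing each arm, without saying what completing means.

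**The concern.** A raw proportion compares arms fairly only if each child has had the same opportunity to reach the event, or if the arms share the same spread of follow-up. The plan secures neither. A child alive, transplant-free and simply too early for Stage III has no stated classification and falls most naturally into the no group, together with children who have died or been transplanted. Those are three different clinical states.

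The arms fill by different routes. Treated children come from the cord-blood collection study, controls mainly from cardiology visits (Section 4.2). Section 1.4 reports only three controls recruited against ten treated in the earlier studies. If controls again lag, they have shorter follow-up at any common data cut, fewer will have reached Stage III, and the bias favours cell therapy. If the treated arm lags, it runs the other way.

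The endpoint is fourth of six in a sequence whose significance is assessed in order without adjustment (Section 7.3, Multiplicity), ahead of transplant listing or death. A spurious result here could therefore carry testing on to the next endpoint.

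Separately, the main test has no baseline term in a non-randomised comparison. The plan's other main efficacy analyses in Section 7.4 have one: ANCOVA with the baseline value, and Cox regression with baseline cardiac function.

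**Working it through.** **The plan's own figure.** No power or error rate is given for Stage III. The only power statement (Section 7.1) concerns cardiac function: effect size 0.57 with 50 per arm, and 0.74 after 40% attrition (50 × 0.6 = 30 per arm). By noncentral t at two-sided 0.05, the effects detectable with 80% power are 0.566 and 0.736, so both figures reproduce. One-sided, power would be about 88%. I therefore use two-sided 0.05.

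**Inputs from the documents.** Up to 50 per arm; follow-up capped at 48 months; study length 72 months; about 70% reaching the Fontan circulation by age 5 (Section 1.1).

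**Assumptions not in the documents.** 70% of children in both arms ever reach Stage III, at a time uniform between 18 and 42 months after Stage II. Accrual is uniform over 24 or 36 months per arm. Controls start 0, 6 or 12 months later. The data cut is at 72 or 60 months from first enrolment. Death and transplant are not modelled separately. There is no treatment effect, and every child not at Stage III by the cut is scored no.

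**Formula.** A child enrolled at month e, in a study cut at month C, has follow-up f = min(48, C − e). The chance of a yes is 0.70 × (f − 18)/24, with the fraction held between 0 and 1. The chi-square rejects when the difference in proportions divided by √(2p(1 − p)/50) exceeds 1.96 in absolute value, where p is the pooled proportion.

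**One row by hand (36-month accrual, 60-month cut, 12-month lag).**
- Arm A: half the children have at least 42 months, so their fraction is 1. The rest run from 42 down to 24 months, with average fraction (1 + 0.25)/2 = 0.625. Expected yes = 0.70 × (0.5 + 0.5 × 0.625) = 56.9%.
- Arm B: 6/36 have at least 42 months (fraction 1), 24/36 run from 42 to 18 months (average 0.5), and 6/36 have under 18 months (0). Expected yes = 0.70 × (0.167 + 0.333) = 35.0%.
- The expected difference is 21.9 points. With p = 0.4595 the standard error is √(2 × 0.4595 × 0.5405/50) = 0.0997, so z is centred on 2.20. About 60% of such trials reject; simulation gives 62%.

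**Results** (at least 20,000 simulated trials per row):

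| Accrual per arm | Data cut | Control lag | Expected yes, A v B | False-positive rate |
|---|---|---|---|---|
| 24 mo | 72 mo | 6 mo | 70% v 70% | 5% |
| 24 mo | 72 mo | 12 mo | 70% v 68% | 5.5% |
| 24 mo | 60 mo | 6 mo | 68% v 61% | 10% |
| 24 mo | 60 mo | 12 mo | 68% v 50% | 44% |
| 36 mo | 72 mo | 6 mo | 69% v 64% | 7% |
| 36 mo | 72 mo | 12 mo | 69% v 57% | 23% |
| 36 mo | 60 mo | 6 mo | 57% v 47% | 19% |
| 36 mo | 60 mo | 12 mo | 57% v 35% | 62% |

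With no lag the rate is 5% throughout.

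**A second model as a check.** Here 75% ever reach Stage III, with time normal about 2.5 or 3.0 years (SD 0.6).
- All followed 4 years: 5%.
- Both arms followed 2–4 years: 5–6%, but the observed proportions fall from 71–75% to 37–54%.
- Arm A 2–4 years, Arm B 1.5–3.5 years: 25–28% with 30 per arm, 39–43% with 50.
- Arm A 2–4 years, Arm B 1–3 years: 75–78% with 30 per arm, 93–95% with 50.
- A log-rank test with censoring stays at 4–6% in every case.

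The inflation therefore needs a follow-up gap between arms and a cut at which some children are still not due. Equal variation in follow-up costs interpretability, not type I error.

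**The case against.** A reader might infer that the plan counts children not yet due, or lost, as failures. No section says so. The missing-data rule in Section 7.3 leaves values missing where carrying the last observation forward is unsuitable, so a lost child might be excluded. What stands is narrower: no rule is given. If the last status of not scheduled were carried forward, a lost child would become a failure.

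A reader might also infer that the false-positive rate is inflated under the plan as it stands. The documents do not support that. Six years overall less four per child leaves 24 months for accrual; with that accrual per arm and a 72-month cut, the rate is about 5% even with a 12-month lag. Section 7.4.2 lets the Sponsor declare endpoints met early, but does not say that follow-up then stops or that Stage III is analysed at that point. If completing the study means follow-up to Stage III work-up, transplant, death or 4 years, the follow-up problem largely goes. Section 1.4 also says the new design has fewer non-standard visits so that controls are easier to recruit.

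Three smaller points stand in part:
- The definition conflict is modest, because Section 6.3.4 links the work-up date to the scheduling of surgery.
- The chi-square is described as a first analysis, with secondary logistic models to follow. Those models address effect modification, and none accounts for follow-up time.
- An unadjusted chi-square is not unique to this endpoint: Section 7.4.5 uses one for adverse events.

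Finally, this is a secondary endpoint on which no power claim rests.

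**Conclusion.** The point holds as a defect in the choice of test and in what the plan leaves undefined. The main test ignores follow-up time and baseline, while Section 7.3 foresees children still in study at the analysis and Section 2 promises baseline adjustment. That not-yet-due children become failures is a likely consequence, not a stated rule.

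The size depends on accrual length, control lag and data cut, none of which is fixed for this endpoint. Under the uniform 18–42 month assumption the effect ranges from negligible (24-month accrual, 72-month cut) to severe (36-month accrual, 12-month lag, 60-month cut). The 70% input is itself approximate: the documents give it by age 5, not by 4 years after Stage II.

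If every child is followed to an end state before analysis, the follow-up bias largely disappears, but the comparison is still unadjusted and non-randomised. The change should be made; it does not threaten the primary endpoint.

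**What to change.** 1. Use one definition in Sections 2, 3.3 and 7.4.4, for example the date of the Stage III pre-operative work-up, which Section 6.3.4 already collects. State the data cut.
2. Replace the chi-square as the main test with time from Stage II surgery to that date, censored at last follow-up or the data cut, with death and transplant as competing events.
3. Describe it by Aalen-Johansen cumulative incidence, including the 48-month estimate by arm.
4. Compare arms with one pre-specified model, for example cause-specific Cox, adjusted for baseline cardiac function, as Section 7.4.4 already does for transplant listing or death. Naming one model fixes what is being estimated.
5. If a raw proportion is also shown, limit it to children whose Stage II surgery was at least 48 months before the data cut, regardless of outcome. With a 60-month cut and a 12-month lag no control would qualify (60 − 12 = 48), so it may not be available at an early cut.

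A 48-month proportion among children whose status is known is not a safe substitute. It keeps early reachers and drops their peers who are still waiting. With no true effect, 36-month accrual and a 12-month lag, it gives 77% v 85% at 72 months and 85% v 100% at 60 months, a spurious difference in the opposite direction.

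Cost: a change of SAP wording, slightly more analysis work and a less simple summary than two percentages. No new data are needed.

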#### **7.4.5 Safety Analysis**

Adverse Events (AEs) will be described by count and frequency, by body system and severity and groups compared using the chi-square test.

The long-term endpoint regarding arrhythmia events and arrhythmia medication will be analyzed regarding safety. Additional adverse events which will be separated out for analyses of their own will be occurrences of bleeding, to such an extent they would be regarded as AEs, decreased cardiac function, and tumor formation.

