## 2 STUDY OBJECTIVES

The purpose of this Phase IIb clinical study is to evaluate the efficacy and safety of autologous UCB-MNC intramyocardial injections into the single, morphological right ventricle of subjects with HLHS or HLHS variants requiring Stage II surgical repair. Thirty to fifty treated subjects and thirty to fifty control subjects will be accrued. Subjects accrued in the treatment arm (Arm A) of this study will be treated with a single dose following successful completion of Stage II surgical repair. Subjects accrued in the control arm (Arm B) of this study will be followed according to the same protocol requirements as the treatment arm but will not receive cell therapy. In the treatment and control arms, surrogate markers of cardiac function, growth, success in reaching Stage III surgical repair pre-operative work-up, time to cardiac transplantation or death, and cumulative days of hospitalization will be recorded and evaluated following the completion of Stage II surgery for up to four years, or until the pre-operative work-up for the Stage III surgical repair has been completed or until cardiac transplant, whichever is first. Development and quality of life as measured by questionnaires will also be monitored. Follow-up surrogate markers and the other variables noted above that are recorded for this study will be compared to baseline and by study arm. The surrogate markers and other variables are described in Section 3 of this protocol.

The objective is to evaluate the short-term (up through 3 months post-Stage II surgical repair) cardiac function, growth, and cumulative days of hospitalization following discharge for the Stage II surgical repair in the treatment and control arms, adjusting for baseline.

This evaluation will also include long-term (6 months and up to 4 years post-Stage II surgical repair or until the pre-operative work-up for the Stage III surgical repair has been completed or until cardiac transplant), cardiac function, growth, ability to reach Stage III surgical repair pre-operative work-up and time to cardiac transplantation or death in the treatment and control arms, adjusting for baseline.

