#### **5.4.2 Product Administration**

Prior to thawing the cells, the identity of both the product and the subject will be confirmed by the study team at the time of enrollment. Following enrollment, trained and delegated team member(s) will thaw the investigational product within the surgical suite. Once thawed, the pre-calculated volume (see Section 5.3) of UCB-MNC product will be loaded into a 1 mL syringe fitted with a 27-gauge butterfly needle and handed off to a site investigator for the cell delivery procedure. The product delivery into the heart tissue should begin within 30 minutes from the beginning of product thawing.

The cell delivery will be performed with injections directly through the epicardial surface of the myocardium, within the free wall of the right ventricle, avoiding epicardial vessels.

Approximately 0.1mL will be delivered per injection site, over 5-10 seconds, followed by 20 seconds of rest prior to needle withdrawal to maximize cell retention within the myocardium. Direct visualization will ensure the cell-based product is entering the myocardial wall and not entering into the ventricular lumen or coronary vessels or being displaced backwards through the injection site upon removal of the needle. The injection sites will be spaced approximately 1 cm apart from each other across the free wall of the right ventricle. Injection sites will be documented on a diagram to record the approximate location of injection sites relative to the coronary vasculature.

Injections will be halted upon complications such as excessive bleeding, ventricular fibrillation, sustained arrhythmias, low blood pressure requiring pharmacological support, or any other concerns of atypical physiology from anyone on the surgical team; the event(s) will be recorded as adverse event(s) on the applicable eCRF. Total volume delivered will be recorded for all partial (less than the planned cell delivery volume) and complete cell deliveries. If a partial cell delivery has occurred, subjects will continue to be followed as planned according to this protocol. Partial cell deliveries along with the specific rationale will be documented on the applicable eCRF but are not considered to be a protocol deviation.

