## **6.2 Enrollment**

### **6.2.1 Enrollment/Cell Delivery:**

- Procedural Timeout (after completion of Stage II surgery)
- Assessment of Eligibility/Enrollment
- AE Assessment
- Cell delivery (treatment group only)
- Telemetry
- High Sensitivity Troponin T at 3 hour +/- 30 min and 6 hour +/- 30 min after enrollment

A site investigator will assess subject eligibility up to the time of enrollment. If there are new test results or conditions identified up to the time of enrollment that causes a subject to no longer be eligible for participation in this study, the subject will be considered a screen failure.

Adverse events will be recorded in the eCRF and subject's study binder following enrollment to document new or worsening symptoms.

During the hospitalization (starting on Day 0), subjects will be monitored with continuous telemetry from enrollment through discharge (or up to 30 days post-surgery if the subject remains hospitalized). The date and time and the type of any arrhythmias that occur via telemetry that are determined to be clinically significant by a study cardiologist will be recorded in the appropriate eCRF and within the subject's study file.

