## 8.6 Causality

Causality of AEs should be assessed using the following relatedness categories:

- Definitely related: the event is *clearly* related the cell therapy product or its delivery procedure
- Probably related: the event is *likely* related the cell therapy product or its delivery procedure
- Possibly related: the event *may be* related the cell therapy product or its delivery procedure
- Unlikely related: the event is *doubtfully* related the cell therapy product or its delivery procedure
- Not Related: the event is *clearly not* related the cell therapy product or its delivery procedure

Adverse events that are unrelated to the cell therapy product or its delivery procedure, but are related to study-required tests and/or procedures, must also be specifically assessed.

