## 8.8 Recording Adverse Events

For the purpose of adverse event recording for this study, investigational sites will document and record in the eCRF in Medidata Rave any adverse event, according to the NCI Common Terminology Criteria for Adverse Events (CTCAE) version 5.0, which meets any of the following criteria:

- It is a serious adverse event
- It is classified by a site investigator as possibly, probably or definitely related to the study drug or its delivery procedure
- It is classified by a site investigator as moderate, severe or life-threatening according to CTCAE version 5.0

Serious adverse events are to be reported to the Sponsor in the AE eCRF in Medidata Rave within 24 hours of site notification of the event. If medical records require review to confirm the details of a serious adverse event, updates will be made accordingly to the serious adverse event report upon medical record review.

The outcome of each adverse event will be recorded in the eCRF.

The Sponsor will be the final adjudicator of adverse events.

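### If section 8.8 governs, non-serious adverse events that stay mild are recorded in practice only in Arm A, yet section 7.4.5 compares the arms at every severity level

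*Combined protocol and SAP*

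**What the plan says.** **Analysis.** Section 7.4.5: "Adverse Events (AEs) will be described by count and frequency, by body system and severity and groups compared using the chi-square test". It adds separate analyses of some events, including bleeding that is severe enough to count as an adverse event. Section 8.5 makes mild the lowest of five severity levels.

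**Recording rule.** Section 8.8 presents itself as the recording rule for the study and lists three criteria, any one of which is enough:
- the event is serious;
- "It is classified by a site investigator as possibly, probably or definitely related to the study drug or its delivery procedure";
- the site investigator grades the event above mild under CTCAE version 5.0.

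**Control arm.** Under section 2, Arm B "will be followed according to the same protocol requirements as the treatment arm but will not receive cell therapy".

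**Other recording passages.** Section 6.2.1, covering both arms: "Adverse events will be recorded in the eCRF and subject's study binder following enrollment to document new or worsening symptoms". Section 6.2.2 says much the same for the hospital stay. Section 8.4 has a general sentence that reported adverse events are recorded by the site. None of the three repeats the 8.8 criteria. Section 4.7, by contrast, defers expressly to Section 8.

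**Telemetry.** Under section 6.2.1, in-hospital arrhythmias "determined to be clinically significant by a study cardiologist will be recorded in the appropriate eCRF". This applies to both arms.

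**The concern.** A between-arm comparison of event counts is fair only if an event of the same kind and grade has the same chance of being recorded in each arm. For mild, non-serious events, the only route in 8.8 depends on an exposure that one arm does not have. For example, a mild post-operative fever judged possibly related is recorded in Arm A, while the same fever in a control child has no route under 8.8. Mild bleeding has the same problem if it is analysed as an adverse event.

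The recording rule alone could therefore produce an Arm A excess in the mild row, in totals over all grades and in body-system tables that include mild events. Its size would depend on how readily investigators in an open-label study choose possibly related. Section 7.4.1 plans five safety and efficacy interim analyses, with results reviewed by the DSMB, so a misleading table could be read more than once before the final analysis.

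**Working it through.** **1. Inputs.** The three criteria come from 8.8, the absence of cells in Arm B from section 2, and the comparison from 7.4.5. Section 7.1 gives 50 subjects per arm and alpha 0.05, for the cardiac function calculation only. The plan gives no figure for adverse event rates, so there is none to reproduce. All event rates below are assumptions.

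**2. Apply 8.8 by type of event.**

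| Event | Route in Arm A | Route in Arm B |
|---|---|---|
| Serious, any grade | serious | serious |
| Non-serious, moderate or worse | severity, or relatedness | severity |
| Non-serious, stays mild, judged at least possibly related | relatedness | none in practice |
| Non-serious, stays mild, judged unlikely or not related | none | none |

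The first two rows are captured alike. The third is not. The words *stays mild* are needed because 8.4 records each change of severity, so the mild phase of an event that worsens can be recorded in either arm. Section 7.4.5 does not say which grade counts.

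**3. Does 8.8 govern?** Its opening words suggest so. Section 1.4 points the same way: it describes modified Phase I reporting criteria meant to focus sites on the more critical events. Neither settles it. If 6.2.1 and 6.2.2 were followed literally, mild events would be recorded in both arms and the asymmetry would go. No passage says which rule prevails.

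**4. Illustration for one table row.** Assume that 8.8 governs, events are tabulated by worst grade, Arm B has no serious event graded mild, and a single row is tested at 0.05. With n per arm and x v 0 subjects:
- Pearson chi-square = 2n·x / (2n − x)
- Yates chi-square = 2n·(x·n − n)² / (n·n·x·(2n − x))
- Fisher two-sided p = 2·C(n, x) / C(2n, x)

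For n = 50:
- x = 4: Pearson 100·4/96 = 4.167, p = 0.041; Yates 100·150²/(2500·4·96) = 2.344, p = 0.126; Fisher p = 0.117.
- x = 6: Pearson 100·6/94 = 6.383, p = 0.012; Yates 100·250²/(2500·6·94) = 4.433, p = 0.035; Fisher p = 0.027.

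Four is the smallest Arm A count with p<0.05 uncorrected; six is the smallest with Yates or Fisher.

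**5. Sensitivity to one Arm B subject.** 6 v 1 gives 0.050 (not below 0.05), 0.117 Yates, 0.112 Fisher. 7 v 1 gives 0.027, 0.065, 0.059. 8 v 1 gives 0.014, 0.036, 0.031. The thresholds rise to 7 uncorrected and 8 with Yates or Fisher.

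**6. How often the threshold is reached.** P(Bin(50, r) ≥ k), where r is the assumed share of Arm A with a recorded mild related event in the row:

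| r | 0 in Arm B, uncorrected (k=4) | 0 in Arm B, Yates/Fisher (k=6) | 1 in Arm B, uncorrected (k=7) | 1 in Arm B, Yates/Fisher (k=8) |
|---|---|---|---|---|
| 5% | 24% | 3.8% | 1.2% | 0.3% |
| 10% | 75% | 38% | 23% | 12% |
| 15% | 95% | 78% | 64% | 48% |

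A recorded 10% needs no true difference between arms. If 40% of both arms have the event and a quarter of those in Arm A are judged possibly related, the recorded rate is 0.40 × 0.25 = 0.10 in Arm A and 0 in Arm B.

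**The case against.** **The numbers rest on a chain of assumptions.** This stands. The rates are assumed, 7.4.5 does not say that single rows are tested, and 0.05 is borrowed from the sample size text. At 4 v 0 the expected counts are 4·50/100 = 2, where the uncorrected test is weak, and splitting by body system makes such counts less likely in any one row. The size is therefore unknown. The asymmetry itself follows from the rule and needs none of these assumptions beyond 8.8 governing.

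**The consequence is limited.** This also stands. The bias runs against the product, the serious and moderate-or-worse comparisons are sound, and the three event-specific stopping rules in 8.11 depend on definite relatedness, not on this test.

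**Three stronger readings are tempting, and the documents do not support them.**
- *Sections 5.4.2 and 8.6 also contradict 8.8.* For complications that halt injections, 5.4.2 says "the event(s) will be recorded as adverse event(s) on the applicable eCRF". But the events it names arise during injection and mostly call for intervention, so nearly all would meet 8.8 as related or as moderate or worse. Section 8.6 says that events unrelated to the product "but are related to study-required tests and/or procedures, must also be specifically assessed"; that requires assessment, not eCRF recording.
- *The mild level is where product events will fall.* All seven product events in 8.10 include a mild grade and three are mild only. Under 8.1.4, however, an event above its listed severity is unexpected, so those grades act as ceilings and do not forecast where events will fall.
- *Phase I shows the size of the problem.* The one definitely related non-serious event described in 1.4 was bleeding controlled with a suture, arguably moderate under 8.5. The visible text does not count possibly or probably related non-serious events, so it supports neither a high nor a low rate.

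**Conclusion.** The concern holds, on the condition that 8.8 governs recording. The mild level, and any total or body-system table that includes it, then compares related mild events in Arm A with a count in Arm B that is close to zero by construction. The direction is toward an apparent Arm A excess, and the amount cannot be estimated from the documents.

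Sections 6.2.1 and 6.2.2 conflict with 8.8 on eCRF recording. Section 8.4 conflicts less sharply, because its general sentence does not name the eCRF. These three need reconciling with 8.8 whichever rule is intended. A reader might infer that the whole safety comparison is unsound; it is not, because 8.8 treats serious and moderate-or-worse events alike in both arms.

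**What to change.** **In 7.4.5:**
- Classify each event by its worst grade.
- Limit between-arm adverse event tests, including totals and body-system tables, to serious events and events of moderate or higher worst grade.
- Describe mild related Arm A events without a test, and state that matching Arm B events are not collected under 8.8. Treat mild bleeding in the same way.
- Compare clinically significant telemetry arrhythmias separately, from their own eCRF data. They are captured alike in both arms, but 6.2.1 does not expressly send them to the adverse event form, so they should not be merged into the adverse event tables.

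**In 6.2.1, 6.2.2 and 8.4:** reconcile the recording sentences with 8.8, for example by the deferral to Section 8 already used in 4.7.

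**Cost.** These are wording changes, plus one separate telemetry table. Mild adverse events lose a formal between-arm test. Keeping that test would mean changing 8.8 to record the chosen mild events in both arms, with more data entry at the sites. A footnote that mild events are selectively recorded would be cheaper, but it would leave an unlike comparison in the table.
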